#### Treatment Options

Anticoagulant therapy is the standard treatment for venous blood clots, preventing new blood clots from forming, and preventing existing blood clots from getting larger and leading to dissolution of the existing clot after successful treatment. Rapid anticoagulation will minimize the risk of thrombus extension and PE in patients with VTE. Treatment duration is determined by the individual patient's clinical presentation. There are a number of factors that influence the type of anticoagulant therapy and treatment duration, including: the presence or absence of one or more risk factors for VTE (i.e., major orthopedic surgery), the acuteness of the thrombotic condition, the risk of recurrence, the risk of bleeding including bleeding due to underlying conditions (e.g., cancer) and issues that can affect compliance (e.g., parenteral versus oral administration and the degree of medical monitoring necessary to ensure efficacy and safety of the treatment).

Current guidelines for the United States (American College of Chest Physicians antithrombotic guidelines) and Europe (European Society of Cardiology), for the acute treatment of VTE recommend the initial administration of a parenteral anticoagulant, usually a low-molecular-weight heparin (LMWH), unfractionated heparin (UFH) or fondaparinux for 5-10 days. Parenteral treatment is followed by treatment with an oral vitamin K antagonist (VKA) such as warfarin that is titrated to a target International Normalized Ratio (INR) of 2 to 3 or dabigatran etexilate or edoxaban. Alternatively rivaroxaban or apixaban may be started immediately or after 1 to 2 days of LMWH, UFH or fondaparinux. Both rivaroxaban and apixaban require dose increases over 3 weeks (for rivaroxaban) or 1 week (for apixaban).

Anticoagulation treatment should last at least 3 months. Longer treatment may be recommended depending on the nature of the initial event (i.e. DVT versus PE), the risk of recurrence and the risk for bleeding [[P12-01518](#), [P14-16368](#)]. Patients with an unprovoked acute VTE should also receive extended anticoagulation therapy assuming that they are not at high risk for bleeding [[P12-01518](#), [P14-16368](#)].

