Optimal treatment duration for acute VTE and the secondary prevention of recurrent VTE is not definitively known. The two terms “acute treatment” and “secondary prevention” are not precisely defined and might overlap. Current guidelines recommend treatment for 3 months over shorter treatment durations [[P12-01518](#), [P14-16368](#)]. An extended duration of anticoagulation treatment should be considered for those patients with the greatest risk of VTE recurrence, i.e., those with an unprovoked DVT and/or PE; recurrent VTE, co-morbidities, such as cancer, chronic inflammation of the peripheral veins, and a strong genetic pre-disposition to thrombosis.

For patients with a chronic risk of recurrent VTE, there is evidence that when oral anticoagulation therapy is stopped, the risk of recurrence will increase to pre-treatment levels [[P08-08095](#), [R09-4888](#)]. Therefore, the decision to continue treatment for prevention of recurrent VTE must consider the risk factors for recurrence as well as any risk factors for bleeding. The risk of bleeding increases in patients with a prior history of bleeding events, the presence of certain co-morbidities (e.g., gastrointestinal ulceration, inflammation or malignancy or other metabolic disorders that might alter hemostasis such as cirrhosis or chronic renal disease or concomitant medications that alter hemostasis (i.e. antiplatelet agents)). These risks must be reviewed periodically, and therefore, treatment decisions should be individualized and periodically reviewed.

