The primary comparative analyses will be based on the actual anticoagulation treatment the patients receive (i.e. “as treated” analysis). Patients who complete the planned anticoagulation treatment prior to one year or discontinue initial anticoagulation treatment permanently will be censored at date of last drug intake + 6 days for both dabigatran etexilate and VKA or at first intake of another relevant anticoagulation treatment, whichever occurs first. A patient is considered to have permanently stopped initial anticoagulation treatment if other relevant anticoagulation treatment is initiated or otherwise dependent on the duration of treatment interruption. Details of the censoring rules will be described in the SEAP.

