7.6 MAIN ANALYSIS

Analyses for the main outcome events are mainly defined for patients in the restricted patient set and, in some occasions for patients in the eligible patient set who took at least once the treatment. In general, recurrent events will be disregarded for the analyses of the outcomes.

Main outcome events – Incidence rates

For the treatment groups incidence rates with 95% CIs, cumulative risks, and KM curves will be calculated on the eligible patient set. Only patients from the eligible patient set that took the prescribed treatment at least once are considered. Patients who complete the planned anticoagulation treatment prior to one year or discontinue initial anticoagulation treatment permanently will be censored at date of last drug intake + 6 days for both DE and VKA or at first intake of another relevant anticoagulation treatment, whichever occurs first. A patient is considered to have permanently stopped initial anticoagulation treatment if other relevant anticoagulation treatment is initiated or if treatment has been interrupted for more than 30 days.

The main analysis of overall incidence rates with 95% confidence intervals, cumulative risks and KM curves will be repeated for the subgroups defined in Section 6.4. A graphical (forest-plot-like) display will additionally be prepared to summarize the subgroup results per outcome on the eligible patient set. Additional subgroup analyses might be conducted as needed.

For all important main and secondary outcomes for patients initiating VKA at baseline, and patients initiating DE at baseline, incidence rates, cumulative risks with 95%-confidence intervals will be calculated by treatment, and for a graphical comparison Kaplan Meier curves

will be plotted. These statistics will be calculated on the restricted patient set, and patients who never took the prescribed treatment will not be included. For the restricted patient set, as a sensitivity analysis, the calculation of incidence rates and cumulative risks will be performed without censoring at permanent discontinuation (intention to treat (ITT) approach). KM curves will be plotted.

Secondary and further outcome events

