In the following if not stated otherwise for all analyses only patients from the restricted patient set are considered.

- 1.) Main analysis of the main outcomes (Major bleeding and clinically relevant non major bleeding, and symptomatic recurrent VTE including VTE-related mortality)

The main analysis will be a PS analysis using overlap weights. A Cox regression model including the overlap weights will be performed. In addition, the main outcomes will be analyzed within the subgroups defined in Section 6.4, when the number of patients per treatment group is at least 500. For the overlap weights analysis each patient in the treatment groups DE and VKA will be weighted proportional to the probability of that

patient being assigned to the opposite treatment group. The weights are called “overlap weights” and are calculated as follows:

$$\begin{aligned} O_{DE} &= 1 - P \\ O_{VKA} &= P \end{aligned}$$

where P is the estimated propensity score of a patient being assigned to the DE treatment group.

To assess baseline imbalance for the overlap weights by ePS, the mean of each covariate of interest will be calculated for patients in each of the treatment groups (DE and VKA). For binary variables, the proportion will be used instead. For categorical variables with more than two categories, dummy binary variables will be derived to represent each category and the proportion calculated for each of the treatments.

The standardized differences will be calculated for the mean for each covariate and the standardized differences (denoted as d) for the mean of a continuous variable is defined [10] as:

$$d = \frac{(\bar{x}_{DE} - \bar{x}_{VKA})}{\sqrt{\frac{s^2_{DE} + s^2_{VKA}}{2}}}$$

where \bar{x}_{DE} and \bar{x}_{VKA} denote the sample mean of the covariate in DE and VKA patients, respectively, while s^2_{DE} and s^2_{VKA} denote the sample variance of the covariate in DE and VKA patients, respectively.

For dichotomous variables, the standardized difference is defined as:

$$d = \frac{(\hat{p}_{DE} - \hat{p}_{VKA})}{\sqrt{\frac{\hat{p}_{DE} * (1 - \hat{p}_{DE}) + \hat{p}_{VKA} * (1 - \hat{p}_{VKA})}{2}}}$$

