where \hat{p}_{DE} and \hat{p}_{VKA} denote the proportion or mean of the dichotomous variables in DE and VKA patients, respectively. This approach described above will be repeated for the same covariates of interest after applying the appropriate overlap weight to each patient based on the ePS and will be presented for each covariate. Note that after weighting, the mean will be used instead of the proportion for binary and categorical variables because the weighting applied will make the variables continuous. After weights will have been applied sample means and variances will be substituted by weighted means and weighted sample variances denoted by

$$\bar{x}_{\text{weight}} = \frac{\sum O_i x_i}{\sum O_i}$$

and

$$s^2_{\text{weight}} = \frac{\sum O_i}{(\sum O_i)^2 - \sum O_i^2} * \sum O_i (x_i - \bar{x}_{\text{weight}})^2$$

where O_i is the weight assigned to the i-th patient.

These unadjusted (i.e., prior to using the overlap weights with ePS adjustment) and adjusted (using overlap weights) standardized differences for the mean will be presented for each covariate.

Balance will then be assessed to determine whether the weighted covariates procedure produces standardized differences for the mean and SD closer to zero (indicating a better balance between the study cohorts) than those of unadjusted covariates. Adjusted standardized differences for any covariate that are greater than 0.25 will potentially warrant re-estimation of the ePS model to improve balance.

- 2.) Sensitivity analysis of the main outcomes (Major bleeding and clinically relevant non major bleeding, and symptomatic recurrent VTE including VTE-related mortality)
 - a.) As sensitivity analysis for the comparison of the two treatment groups, dabigatran etexilate and VKA, with regards to the main outcomes a multivariable Cox regression model will be performed. The multivariable Cox regression model will include the variables given in [Table 7.6: 2](#). In case of model convergence issues due to limited number of events, some variables may be removed from the model as deemed necessary.

Table 7.6: 2 Variables for Cox regression model

Variable	Comment	Potential for missing values and implications
Age	continuous	Very unlikely
BMI	continuous	Missing will be imputed
Trauma or surgery	True or False (CRF categories, medical history and concomitant diseases will be manually reviewed – 3 month time window)	N/A

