Immobilization	True or False (CRF categories, medical history and concomitant diseases will be manually reviewed (past and concomitant))	N/A
Thrombophilia	True or False (CRF categories, medical history and concomitant diseases will be manually reviewed (past and concomitant))	N/A
Pregnancy and peri-partum period	True or False (CRF categories, medical history and concomitant diseases will be manually reviewed (3 month time window))	N/A

Concomitant use of aspirin	True or False (concomitant medication and other VTE therapies will be manually reviewed (concomitant))	N/A
Concomitant use of clopidogrel	True or False (concomitant medication and other VTE therapies will be manually reviewed (concomitant))	N/A
Estrogen therapy	True or False (concomitant medication and other VTE therapies will be manually reviewed (3 month time window))	N/A
Concomitant cancer	True or False (CRF categories, medical history and concomitant diseases will be manually reviewed (concomitant))	N/A
Hypertension	True or False (CRF categories, medical history and concomitant diseases will be manually reviewed (concomitant))	N/A
History of previous VTE	True or False (CRF categories, medical history and concomitant diseases will be manually reviewed (regardless of timing))	N/A
History of major bleeding or prior gastrointestinal bleed	True or False (medical history and concomitant diseases will be manually reviewed (regardless of timing))	N/A
Chronic renal disease	True or False (CRF categories, medical history and concomitant diseases will be manually reviewed (concomitant))	N/A

Patients who complete the planned anticoagulation treatment prior to one year or discontinue initial anticoagulation treatment permanently will be censored at date of last drug intake + 6 days for both dabigatran etexilate and VKA or at first intake of another relevant anticoagulation treatment, whichever occurs first. A patient is considered to have permanently stopped initial anticoagulation treatment if other relevant anticoagulation treatment is initiated or if treatment has been interrupted for more than 30 days.

Multiple imputation methods (e.g. the fully conditional specification method) will be used to impute both continuous and categorical variables appropriately with arbitrary missing patterns.

- b.) In addition, Cox regression analysis (based on the main analysis model) will be performed without censoring at permanent discontinuation (intention to treat (ITT) approach).

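### The main as-treated Cox model censors at stopping with weights that balance the arms at baseline only; if risk-related stopping differs between DE and VKA, both main hazard ratios could be biased, and the planned checks cover this only in part

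*Protocol*

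**What the plan says.** **What drives duration.** Protocol 7.2, Treatment Options, ties length of therapy to the index event and to risk: "Longer treatment may be recommended depending on the nature of the initial event (i.e. DVT versus PE), the risk of recurrence", and also bleeding risk. It adds that "the decision to continue treatment for prevention of recurrent VTE must consider the risk factors for recurrence as well as any risk factors for bleeding" and that these risks are to be reviewed from time to time. Inclusion criterion 4 asks only for planned therapy of at least 3 months, so many patients may stop within the one-year window.

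**What the main analysis does.** Protocol 9.7.2.1: "The primary comparative analyses will be based on the actual anticoagulation treatment the patients receive". Patients who finish early or stop for good "will be censored at date of last drug intake + 6 days for both dabigatran etexilate and VKA", or at a switch if that comes first. SAP (Objective 2) 7.6 repeats the rule ("discontinue initial anticoagulation treatment permanently will be censored at date of last drug intake + 6 days for both DE and VKA") and defines a permanent stop as a switch or "if treatment has been interrupted for more than 30 days". For both main outcomes, item 1 of 7.6 says "A Cox regression model including the overlap weights will be performed". The weights are 1 − P for DE and P for VKA, where P is the propensity score from the Table 7.6:1 covariates. SAP 6.7 limits these to data up to the start of treatment.

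**What checks are planned.**
- 2a: under the same censoring, "The multivariable Cox regression model will include the variables given in" Table 7.6:2.
- 2b: the main model without censoring at discontinuation (ITT).
- SAP 7.3 summarises persistence, and 7.6 tabulates the proportion censored up to 3, 3-6, 6-12 and beyond 12 months.
- Protocol 9.2.4 keeps patients who stop in follow-up.

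**The concern.** Censoring at stopping is harmless when, within each arm, those who stop have the same outlook as those who stay. By the protocol's own account they do not: continuation is decided on the risks that the two main outcomes measure. Overlap weights make the arms alike at the start of treatment and do nothing about who is still at risk in month 9. If low-risk patients leave the VKA arm faster than the DE arm, or the reverse, the later risk sets differ in prognosis even when baseline balance is perfect. The as-treated hazard ratio then mixes the drug effect with the difference in stopping practice.

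The documents give some reason to think practice could differ. Protocol 7.2 lists the amount of monitoring a drug needs among the influences on both choice and duration of therapy, and protocol 9.9 says the drugs differ in INR monitoring, cost and reimbursement. The readable limitations text in protocol 9.9 does not discuss informative censoring, SAP 7.4 only refers back to the protocol, and SAP 7.6 contains no model for stopping.

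**Working it through.** **1. The plan's own figure.** Protocol Table 9.5:2, first row: VKA rate 7.7%, HR 0.69, 90% power, one-sided alpha 0.025, 15% loss, Freedman formula, N = 5000. Events = (1.960 + 1.282)² × [(1 + HR)/(1 − HR)]². With HR 0.685, which prints as 0.69, this is about 301. With loss as a competing exponential hazard, the mean one-year event probability is 0.0602, and 301/0.0602 ≈ 5000. The DE rate is 1 − 0.923^0.685 = 5.3%, as printed. The study size is not in question.

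**2. Set-up for the bias.** The documents give no stopping rates, so every stopping input is an assumption. There are two risk classes, 50:50 in both arms (perfect baseline balance), with the event rate R times higher in the high-risk class. The overall one-year VKA rate is 7.7%. The low-risk yearly hazard λ solves ½(1 − e^(−λ)) + ½(1 − e^(−Rλ)) = 0.077; for R = 3, λ ≈ 0.040. Nobody stops before month 3. After that the fraction still on drug in arm a, class c is G(t) = (1 − s)^((t − 3)/9), where s is the share stopping by month 12.

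With S the event-free fraction, the at-risk fraction is Y_a(t) = ½ Σ_c S·G and the event density D_a(t) is the same sum with each term multiplied by its hazard. The large-sample Cox HR is e^β, where ∫ [D_1 − (D_0 + D_1)·Y_1e^β/(Y_1e^β + Y_0)] dt = 0.

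**3. The mechanism by hand.** R = 3, true HR 1.00, stopping low/high: VKA 70%/30%, DE 50%/50%. Ignoring events, at month 12 the VKA arm retains 0.15 low and 0.35 high (70% high-risk); DE retains 0.25 and 0.25 (50%). Mean hazards relative to the low class are 0.3 × 1 + 0.7 × 3 = 2.4 and 0.5 × 1 + 0.5 × 3 = 2.0. The apparent ratio at month 12 is 2.0/2.4 = 0.83, against 1.00 up to month 3. Over the whole year the Cox limit is 0.94.

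**4. Results, true HR 1.00.**

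| Share stopping by month 12 (low/high risk) | R = 2 | R = 3 | R = 5 |
|---|---|---|---|
| Unrelated to risk: VKA 30/30, DE 60/60 | 1.00 | 1.00 | 1.00 |
| Risk-related, same in both: 70/30 | 1.00 | 1.00 | 1.00 |
| VKA 60/40, DE 50/50 | 0.98 | 0.97 | 0.96 |
| VKA 70/30, DE 50/50 | 0.96 | 0.94 | 0.92 |
| VKA 60/20, DE 85/45 | 1.03 | 1.04 | 1.05 |
| Opposite: VKA 70/30, DE 30/70 | 0.92 | 0.89 | 0.85 |

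With a true HR of 0.69 and R = 3, rows 2, 4, 5 and 6 give 0.69, 0.65, 0.72 and 0.61. An assumed 3% event rate, as might suit recurrence, gives practically the same biases.

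**5. Direction.** A second set lets patients stop at months 3 and 6, with R = 2 to 4 and a flat or front-loaded hazard. Moderate contrast: VKA low-risk 50%/40%, high-risk 20%/20%; DE low-risk 35%/35%, high-risk 30%/25%. The HR is 0.92-0.98. Stronger contrast: VKA 70%/50% and 20%/20%; DE 40%/40% and 35%/30%. The HR is 0.86-0.95.

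There low-risk patients stop more, which suits recurrence. For bleeding, the protocol reserves extended therapy after unprovoked VTE for those not at high bleeding risk, so high-risk patients may stop more. Exchanging the class rates gives 1.03-1.09 (moderate) and 1.05-1.20 (stronger).

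**6. What the planned checks recover.** A Cox model that includes the risk marker returns 1.00 at a true HR of 1.00, because within a class stopping no longer depends on risk. So 2a works for any driver it contains. Censoring weights on the marker also return 1.00, by construction.

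ITT behaves differently. With R = 3, a true HR of 0.69 and identical stopping (70/30), where as-treated is unbiased, ITT gives 0.71 for bleeding (off-drug hazard assumed 0.2 times VKA) and 0.81 for recurrence (assumed 3 times VKA). A gap between as-treated and ITT therefore does not show that censoring is at fault.

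**7. Coverage of 2a.** Table 7.6:2 has cancer, previous VTE, thrombophilia, trauma or surgery, immobilization, prior major or gastrointestinal bleeding, chronic renal disease, aspirin and clopidogrel. It does not have index event type, which protocol 7.2 names as a driver of duration and Table 7.6:1 includes, nor planned duration, which protocol 9.3.1.1 collects. All its variables are baseline values, so it cannot follow a periodic review of risk.

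**The case against.** The strongest reply is that the bias at the null needs stopping that is related to risk and also differs by drug. Protocol 7.2 describes one set of considerations for anticoagulation in general; no readable text says the two drugs are stopped by different habits. That stands, and so the bias is a possibility and not a finding.

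Second, the plan is not blind to the problem. 2a keeps the same censoring and needs independence only given its covariates, which include most of the named drivers; a gap between 2a and the main HR would be a warning. 2b avoids the censoring, and it has data because follow-up continues. Persistence and the proportion censored are already reported. This also stands, within limits. 2a lacks the index event and post-baseline changes, and because it changes the confounding adjustment at the same time, a gap has more than one explanation. 2b answers a different question.

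Third, a bleed or recurrence that leads to stopping is counted as an event first and is not informative censoring. Correct; the calculation does not use such cases. Fourth, protocol 9.7.1 calls the analyses exploratory. That lowers the stakes, but the assumption still sits unstated under both main hazard ratios.

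**Conclusion.** The gap is real but limited. The plan's own background makes stopping depend on prognosis, the main model censors at stopping, and its weights act at baseline only. If risk-related stopping differs between drugs, the main hazard ratios could be off by about 2-8% under mild to moderate patterns and by about 15-20% in extreme ones (0.85 to 1.20 when the truth is 1.00), in either direction. If stopping is the same in both arms there is no bias at the null. All of this rests on assumed stopping rates and a two-class risk marker.

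A reader might infer that stopping habits do bias both hazard ratios and that the planned output would hide it. The documents support neither: they give no stopping rates and no difference by drug, and 2a would expose bias from the drivers it lists. Nor should an as-treated HR of 0.86 from these scenarios be set against the design HR of 0.69: that value comes from low-risk patients stopping more, while 0.69 belongs to bleeding, where the opposite pattern is at least as plausible.

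Statements about what is absent cover the readable text only; SAP 5.3, 6.4 and 7.7 and protocol 9.7.2.2 are not available. This is a low-cost improvement, not a fault that invalidates the plan.

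**What to change.** 1. Add index event (DVT, PE, both) to Table 7.6:2.
2. In SAP 7.6 item 2, state the independent-censoring assumption and add sensitivity analysis 2c for both main outcomes: the main Cox model with each overlap weight multiplied by a stabilised inverse-probability-of-censoring weight. Estimate that weight separately by drug, over intervals split at months 3 and 6, from the Table 7.6:1 covariates, planned duration, and the concomitant disease, co-medication and laboratory data updated at each contact (protocol Table 9.3.1:2). Pre-specify weight truncation and robust or bootstrap standard errors.
3. Extend the persistence summary to time to stopping and its reasons, by drug and baseline risk. State in advance that if 2a or 2c differs materially from the main HR, the conclusion will not rest on the main HR alone.

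Cost: SAP wording and programming, with no new data or patients. Intervals in 2c will be somewhat wider. Censoring weights give no protection against unmeasured reasons for stopping, and the SAP should say so.
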